**Appendix 1. Schedule of Assessments**

Period	Screen	Treatment																			Follow-Up	
		1	2	3	4	5	6	7	8	9	10	11	12	13	14	15	16	17	18	19	20	PTx a
Visit	1	2	3	4	5	6	7	8	9	10	11	12	13	14	15	16	17	18	19	20		
Week		0	2	4	6	10	11	14	17	20	23	26	30	34	38	42	46	50	54	58		
Study Day	-30 to -1	1	15	29	43	71	78	99	120	141	162	183	211	239	267	295	323	351	379	407		
Visit Window (±)			±3	±3	±3	±2	±3	±5	±5	±5	±5	±5	±5	±5	±5	±5	±5	±5	±5	±5	±3	±3
Written Informed Consent	X																					
Medical History & Demographics	X																					
Crohn's Disease & Treatment History	X																					
12-lead ECG	X					X						X									X	X b
Review of Inclusion/Exclusion Criteria	X	X																				
Complete Physical Exam c	X																					
Symptom-directed Exam e (as needed)		X	X	X	X	X	X	X		X		X		X		X		X		X	X	X
Vital Signs	X	X	X	X	X	X	X	X		X		X		X		X		X		X	X	X
Height	X																					
Weight	X	X	X	X	X	X		X		X		X		X		X		X		X	X	X
Adverse Events	X	X	X	X	X	X	X	X		X		X		X		X		X		X	X	X
Concomitant Medications	X	X	X	X	X	X	X	X		X		X		X		X		X		X	X	X
Randomization		X					X															

Period	Screen	Treatment																			Follow-Up	
		1	2	3	4	5	6	7	8	9	10	11	12	13	14	15	16	17	18	19	20	PTx a
Week		0	2	4	6	10	11	14	17	20	23	26	30	34	38	42	46	50	54	58		
Study Day	-30 to -1	1	15	29	43	71	78	99	120	141	162	183	211	239	267	295	323	351	379	407		
Visit Window (±)			±3	±3	±3	±2	±3	±5	±5	±5	±5	±5	±5	±5	±5	±5	±5	±5	±5	±5	±3	±3
Study Drug Dispensing		X		X			X	X		X		X		X		X		X				
Ileocolonoscopy (with Biopsies) d	X					X															X	
Local Endoscopic Assessment e	X					X															X	
SES-CD	X					X															X	
CDAI f	X		X	X	X	X		X		X		X		X		X		X		X		X
PRO2 f	X		X	X	X	X		X		X		X		X		X		X		X		X
Abdominal pain assessment g	X	X	X	X	X	X		X		X		X		X		X		X		X		X
Anchor Questions	X																					
Patient Global Impression Scales h		X				X															X	
eDiary instruction & review i	X	X	X	X	X	X	X	X		X		X		X		X		X		X		X
Stool for C. diff toxin, pathogenic E. coli , Salmonella spp, Shigella spp, Campylobacter spp or Yersinia spp testing j	X																					

Period	Screen	Treatment																			Follow-Up	
		2	3	4	5	6	7	8	9	10	11	12	13	14	15	16	17	18	19	20	PTx a	ET
Visit	1																					
Week		0	2	4	6	10	11	14	17	20	23	26	30	34	38	42	46	50	54	58		
Study Day	-30 to -1	1	15	29	43	71	78	99	120	141	162	183	211	239	267	295	323	351	379	407		
Visit Window (±)			±3	±3	±3	±2	±3	±5	±5	±5	±5	±5	±5	±5	±5	±5	±5	±5	±5	±3	±3	
Stool O&P j	X																					

[figure not shown]

Urine drug screen k	X																					
Urinalysis	X	X				X														X		
Pregnancy Test l	X	X		X	X	X		X	X	X	X	X	X	X	X	X	X	X	X	X	X	X
TB m	X																					
Chest x-ray n	X																					
HBV, HCV, HIV screening o	X																					
HBV DNA monitoring (Japan) p				X	X	X		X	X	X	X	X	X	X	X	X	X	X	X	X	X	
HBV DNA monitoring (other regions) p						X				X				X				X		X		
Hematology	X	X	X	X	X	X		X		X		X		X		X		X		X	X	X
Chemistry	X	X	X	X	X	X		X		X		X		X		X		X		X	X	X
Lipid profile (fasting) q		X				X						X								X		X

[figure not shown]

[figure not shown]
Period	Screen	Treatment																			Follow-Up	
Visit	1	2	3	4	5	6	7	8	9	10	11	12	13	14	15	16	17	18	19	20	PTx a	ET
Week		0	2	4	6	10	11	14	17	20	23	26	30	34	38	42	46	50	54	58		
Study Day	-30 to -1	1	15	29	43	71	78	99	120	141	162	183	211	239	267	295	323	351	379	407		
Visit Window (±)			±3	±3	±3	±2	±3	±5	±5	±5	±5	±5	±5	±5	±5	±5	±5	±5	±5	±5	±3	±3
Serum immunoglobulin		X		X		X						X								X	X	X
Blood TCR/BCR repertoire sample TP		X		X		X						X								X		

PK collection (sparse) s				X		X						X									X		
-------------------------------------	--	--	--	---	--	---	--	--	--	--	--	---	--	--	--	--	--	--	--	--	---	--	--

PK substudy u				X																			
--------------------------	--	--	--	---	--	--	--	--	--	--	--	--	--	--	--	--	--	--	--	--	--	--	--

- a. The Post-Treatment (PTx) visit should occur 30 days after the last dose of study drug. Only subjects who roll over into the LTE study (GS-US-419-3896/GLPG0634-CL-310) will not complete PTx assessments.
- b. For subjects who terminate prior to Week 10.
- c. A complete physical examination (PE) including, vital signs, body weight, and height will be performed at screening. A symptom directed PE may be done at other time points.
- d. Once a subject meets all other eligibility criteria (centrally calculated CDAI, PRO2 and labs), perform the screening full video ileocolonoscopy with biopsies within 14 days prior to Day 1 visit.
- e. The investigator (ie local endoscopist) may enter endoscopic assessment data based on the SES-CD in the eCRF (see Appendix 5). The locally read SES-CD score may not be used for eligibility or assessing endoscopic response for primary efficacy analysis, and it is not a substitute for the centrally read score, CCI [REDACTED]
- f. The screening CDAI will be used to determine subject eligibility for the study on Day 1. The CDAI patient reported outcomes of stool frequency and abdominal pain will be used to derive the PRO2 score. [REDACTED]
- g. [REDACTED]
- h. Patient global impression change (PGI-C) should be assessed at Weeks 10 and 58 only. Patient global impression of severity (PGI-S) should be assessed at Day 1, Weeks 10 and 58.
- i. Subjects should begin filling out the e-Diary the day of their initial screening visit and continue to fill it out throughout the remainder of the study.
- j. Stool samples should be collected to rule out infectious causes when disease worsens.
- k. Positive cocaine test disqualifies subject; positive amphetamines, barbiturates, benzodiazepines, and opioids require medical monitor review.
- l. All females meeting the childbearing potential criteria must have a serum pregnancy testing at screening and a urine pregnancy test must be completed in clinic every 4 weeks at a minimum. If any pregnancy test is positive, study drug should be immediately interrupted and the subject should have a serum pregnancy test in clinic.
- m. Proof of no active or untreated latent TB at screening. Subjects who are diagnosed with latent TB at screening must initiate an adequate course of prophylaxis as per local standard of care for a minimum of 4 weeks prior to randomization. Subject may initiate study drug dosing only after consultation with the medical monitor.
- n. Chest x-ray (views as per local guidelines) taken at screening or within the 3 months prior to screening (with the report or films available for investigator review) without evidence of active or latent TB infection
- o. Hepatitis B surface Ag, surface Ab and core Ab, reflex HBV DNA, Hepatitis C Ab, reflex HCV RNA, HIV Ag/Ab, reflex HIV 1/2 Ab at Screening (Protocol Section 6.2.1).
- p. In Japan, subjects with negative HBsAg, positive HBcAb and/or positive HBsAb at Screening require HBV DNA monitoring every 4 weeks in accordance with local guidelines (Protocol Section 6.2.1). In other regions, subjects with negative HBsAg and positive HBcAb require HBV DNA monitoring every 3 months in accordance with local guidelines (Protocol Section 6.2.1)
- q. Fasting means no food or drink, except water, for 8 hours
- r. TCR: T-cell receptor; BCR: B-cell receptor.
- s. This PK sample at Weeks 10 and 58 are collected at pre-dose (within 2 hours prior to dosing). The PK sample at Week 4 is collected post-dose dose (at least 30 minutes and up to 3 hours after study drug dosing . For this visit, it is preferred that study drug dosing is in clinic. The PK sample at Week 26 can be collected at any time without regard to dosing. For these visits, the time of dose taken on the day of and the dose taken prior to the PK sample being drawn will be noted in the eCRF.
- t. CCI [REDACTED]
- u. Subjects who consent to optional PK substudy will have an additional plasma PK sample at any single visit from Week 2 to 10, collected pre-dose and at 0.5, 1, 2, 3, 4 and 6 hours after supervised dosing in the clinic. For all visits with PK sampling, the time of dose taken prior to and on the day of visit will be noted in the eCRF
- v. CCI [REDACTED]
- w. [REDACTED]

## Appendix 2. List of Biologics for CD Treatment

The drug names of biologics considered as CD treatment are listed below.

No.	Drug Class	Drug Name
1	TNF- $\alpha$ antagonist	Adalimumab
2	TNF- $\alpha$ antagonist	Certolizumab/Certolizumab Pegol
3	TNF- $\alpha$ antagonist	Infliximab
4	TNF- $\alpha$ antagonist	TNF- $\alpha$ antagonist biosimilar (to adalimumab, Certolizumab/Certolizumab Pegol, or infliximab)
5	Integrin antagonist	Natalizumab
6	Integrin antagonist	Vedolizumab
7	Interleukin antagonist	Ustekinumab

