**Stratification Factors (Cohort A, Biologic-Naïve and Biologic-Experienced Induction Study)**

- History of exposure to no biologic agent, one biologic agent, or more than one biologic agent
- Concomitant use of oral, systemically absorbed corticosteroids (eg, prednisone) at Day 1, (Yes or No)
- Concomitant use of immunomodulators (eg, 6-mercaptopurine [6-MP], azathioprine, MTX) at Day 1, (Yes or No)

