#### **4.3.2. Exclusion Criteria for Biologic-Naïve Subjects Enrolled in Cohort A**

Biologic-Naïve subjects who meet any of the following exclusion criteria are not eligible for Cohort A.

- 1) Prior or current use of TNF $\alpha$  antagonist, including (but not limited to) infliximab, adalimumab, golimumab, certolizumab, or biosimilar agent
- 2) Prior or current use of vedolizumab at any time
- 3) Prior or current use of ustekinumab at any time

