**Table 5-1. Prohibited Concomitant Medications**

Drug Class	Agents Disallowed	Prohibited Period
Strong P-gp Inducersa		
Anticonvulsants	Phenobarbital, phenytoin, carbamazepine,	30 days prior to screening through the end of the study
Antimycobacterials	Rifabutin, rifapentine, rifampin	
Herbal/Natural Supplements	St. John's wort, danshen (Salvia Miltiorrhiza)	
Prohibited IBD Medications		
Corticosteroids	Dose equivalent to > 30 mg/day of prednisone	30 days prior to screening through the end of the study
TNF $\alpha$ antagonist	Infliximab, adalimumab, golimumab, certolizumab, or biosimilar agent	8 weeks prior to screening d through the end of the study
Integrin antagonist	Vedolizumab and natalizumab	8 weeks prior to screening d through the end of the study
Interleukin antagonist	Ustekinumab	12 weeks prior to screening d through the end of the study
Other (non-biologic)	Cyclosporine, thalidomide, tacrolimus, leflunomide, and any investigational agent	30 days prior to screening through the end of the study
	Any JAK inhibitor	Any time before and through the end of the study
Investigational biologics	Any investigational biologic agent	8 weeks prior to screening through the end of the study (or at least 5 half lives)
Lymphocyte-depleting therapies	Alemtuzumab, cyclophosphamide, total lymphoid irradiation, rituximab, and any other lymphocyte depleting therapy	Any time before and through the end of the study
Other Prohibited Medications		
Chronic Nonsteroidal Anti-inflammatory Drugs (NSAIDs) b	Aspirin, ibuprofen, naproxen, diclofenac, indomethacin, COX-2 inhibitors	From screening through the end of the study
Other biologics c	Antibody based or other systemic biologics, eg, denosumab, trastuzumab	Requires medical monitor consultation

Abbreviations: COX-2=Cyclooxygenase-2; JAK=Janus Kinase; NSAID=Nonsteroidal Anti-inflammatory Drugs; TNF $\alpha$ =tumor necrosis factor-alpha

- a May decrease study drug exposure and are excluded to avoid potential reduction in study drug activity. PK results indicate that filgotinib is a P-gp substrate, as a single dose of 200 mg itraconazole (a potent P-gp inhibitor) increased filgotinib Cmax by 64% and AUCinf by 45% and had no effect on the major, active metabolite GS-829845.

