### 3.3. Strata and Covariates

Subjects will be randomly assigned to treatment groups via IWRS using a stratified randomization schedule into each individual study (Cohort A Induction, Cohort B Induction, and Maintenance). Details of the randomization ratio and stratification variables for each study are provided in Section 1.2.

If there are discrepancies in stratification factor values between the IWRS and the clinical database (eCRF data), the baseline values recorded in the clinical database will be used for analyses. For the derivation of concomitant medication use at Day 1, the start date of such medication should be before or on the same date of the first dose of study drug and with either the stop date of such medication being on or after the first dose of study drug or with “ongoing” status.

Stratification factors will be used as covariates in evaluating efficacy endpoints, as specified in Section 6.

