##### Cohort A Induction Study:

- Number of prior exposures to biologic agent (0, 1, > 1) as listed in [Appendix 2](#)
- Concomitant use of oral, systemically absorbed corticosteroids at Day 1
- Concomitant use of immunomodulators at Day 1

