##### Cohort B Induction Study:

- Number of prior exposures to biologic agent ( $\leq 1$ , > 1) as listed in [Appendix 2](#)
- Concomitant use of oral, systemically absorbed corticosteroids at Day 1
- Concomitant use of immunomodulators at Day 1

For the Maintenance Study, a stratified CMH test will be used to compare the treatment effect between a filgotinib dose group and placebo among the subjects from Induction Cohorts A and B combined being treated with the same dose of filgotinib. The CMH test will be stratified by the following factors:

- History of exposure to a biologic agent, (Yes or No)
- Concomitant use of oral, systemically absorbed corticosteroids at maintenance baseline
- Concomitant use of immunomodulators at maintenance baseline

Stratification factors based on the clinical database will be used for the analysis. The stratified CMH chi-square p-value for each of the above comparison will be provided. Strata with low numbers of subjects might be aggregated for the analysis. The 2-sided 95% CI of clinical remission rate by CDAI and endoscopic response rate based on normal approximation method with a continuity correction will be provided for each treatment group. In addition, stratified proportion difference along with its 95% 2-sided CI using stratum-adjusted Mantel-Haenszel (MH) approach {Koch 1989} for each comparison will be provided as follows:

The stratified point estimates for difference in proportion of subjects achieving an endpoint between each filgotinib (F) treatment group and the placebo (P) group will be calculated following formula (1).

$$\hat{p}_F - \hat{p}_P = \frac{\sum W_h d_h}{\sum W_h} \quad (1)$$

where  $d_h = \hat{p}_{Fh} - \hat{p}_{Ph}$  is the difference in the proportion of subjects who achieved the endpoint between the filgotinib group and the placebo group in stratum  $h$  ( $h = 1, 2, \dots, K$ ), and  $W_h = \frac{n_{Fh}n_{Ph}}{n_{Fh}+n_{Ph}}$  is the weight based on the harmonic mean of sample size per treatment group for each stratum where  $n_{Fh}$  and  $n_{Ph}$  are the sample sizes of the filgotinib group and the placebo group in stratum  $h$ , respectively.

The 95% stratum-adjusted MH CIs will be calculated following formula (2).

$$\hat{p}_F - \hat{p}_P \pm Z_{1-\alpha/2} \cdot SE(\hat{p}_F - \hat{p}_P) \quad (2)$$

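### SAP Appendix 2 omits golimumab, so some golimumab-treated subjects are analysed in too low a prior-biologic stratum, and those with no other biologic as naive

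*SAP*

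**What the plan says.** **The counting rule.** SAP Section 6.2.4 defines the Cohort A CMH factor as "Number of prior exposures to biologic agent (0, 1, > 1) as listed in" Appendix 2. The Cohort B factor, "Number of prior exposures to biologic agent" in categories ≤1 and >1, also refers to that appendix. So do the Cohort A, Cohort B and pooled A+B prior-exposure subgroups in Section 6.2.7, and the baseline summaries of number of prior biologics and prior TNF antagonist use in Section 5.2.

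**The list.** Appendix 2 opens with "The drug names of biologics considered as CD treatment are listed below". It has seven rows: adalimumab, certolizumab, infliximab, a biosimilar row, natalizumab, vedolizumab and ustekinumab. There is no row for other agents, and the biosimilar row is limited: "biosimilar (to adalimumab, Certolizumab/Certolizumab Pegol, or infliximab".

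**The protocol.** Section 4.3.2 excludes from the biologic-naive group anyone with prior or current TNF antagonist use, "including (but not limited to) infliximab, adalimumab, golimumab, certolizumab, or biosimilar agent". Table 5-1, under prohibited IBD medications, gives the TNF antagonists as "Infliximab, adalimumab, golimumab, certolizumab, or biosimilar agent". The Cohort A randomization factor in Section 3.3 is "History of exposure to no biologic agent, one biologic agent, or more than one biologic agent", with no list attached.

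**Which value is analysed.** Where IWRS and the clinical database disagree on a stratification factor, SAP Section 3.3 says "the baseline values recorded in the clinical database will be used for analyses".

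**The concern.** The protocol and the SAP use different definitions of a prior biologic. A subject whose only biologic was golimumab cannot be enrolled as naive under the protocol, yet the SAP count puts that subject in the zero stratum. A site that counts golimumab correctly at randomization has its entry replaced by a database count that leaves golimumab out.

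At stake are the meaning of the zero category in the Cohort A primary analysis, the naive versus experienced subgroup results, the baseline description of treatment history, and the match between analysis strata and randomization strata. The SAP adds the pooled A+B subgroup specifically to compare subjects with and without biologic experience, so a clean zero group matters there.

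**Working it through.** The plan gives no figure to reproduce. The check is one of classification, followed by an illustration of the effect on the test.

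**Step 1. Is golimumab captured anywhere in Appendix 2?** It is not named, there is no catch-all row, and the biosimilar row covers only three other products. Neither document adds it back.

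**Step 2. Can such subjects enrol?** Yes. In both cohorts one entry route is intolerance to any TNF antagonist (protocol Sections 4.3.3 and 4.4.1). Cohort A also admits subjects who stopped an agent for reasons other than failure or intolerance. The inadequate-response route names only infliximab, adalimumab, certolizumab or a biosimilar, so golimumab-only entry is narrow. Golimumab combined with a listed agent is not restricted in this way.

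**Step 3. Map each exposure pattern to the SAP categories.** True count = listed agents + 1. Appendix 2 count = listed agents. Arrows run from the true category to the Appendix 2 category.

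| Prior agents | True count | Appendix 2 count | Cohort A CMH (0, 1, >1) | Cohort B CMH and subgroup (≤1, >1) | Cohort A and pooled subgroups (0, ≥1) | Baseline table (0, 1, 2, ≥3) |
|---|---|---|---|---|---|---|
| Golimumab only | 1 | 0 | 1 → 0 | ≤1, unchanged | ≥1 → 0 | 1 → 0 |
| Golimumab + 1 listed | 2 | 1 | >1 → 1 | >1 → ≤1 | ≥1, unchanged | 2 → 1 |
| Golimumab + 2 listed | 3 | 2 | >1, unchanged | >1, unchanged | ≥1, unchanged | ≥3 → 2 |
| Golimumab + 3 listed | 4 | 3 | >1, unchanged | >1, unchanged | ≥1, unchanged | ≥3, unchanged |

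Only the first two rows move a CMH stratum, and only the first puts an experienced subject in a naive category.

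**Step 4. Effect on the primary test (illustration).** All inputs except the 220 per arm are assumptions:
- proportions with 0, 1, 2 and 3 prior biologics: 50%, 25%, 15% and 10%
- placebo response: 30%, 23%, 17% and 17% respectively
- treatment difference: 15 points throughout
- golimumab share among experienced subjects: 2% to 20%
- 3,000 runs, with a CMH test on the three biologic strata only

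| Golimumab share | Power, true strata | Power, Appendix 2 strata | Type I error, true | Type I error, Appendix 2 |
|---|---|---|---|---|
| 2% | 92.7% | 92.6% | 5.5% | 5.5% |
| 5% | 92.6% | 92.7% | 5.4% | 5.4% |
| 10% | 91.2% | 91.3% | 4.5% | 4.7% |
| 20% | 92.8% | 92.7% | 4.8% | 5.0% |

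The power differences are about 0.1 percentage point and go in both directions. For scale, the simulation error of one power figure is √(0.927 × 0.073 / 3000) ≈ 0.5 points. The test behaves the same under either set of strata.

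**The case against.** **The omission may be intended.** Appendix 2 is headed as biologics for CD treatment. The protocol Background names three TNF antibodies marketed for CD (infliximab, adalimumab and certolizumab), and the inadequate-response criteria name the same three. The golimumab references sit in a broad exclusion and in a table headed IBD. An exclusion list and a counting rule need not match, and the ≤1 category in Cohort B already leaves room for a zero count.

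This makes a deliberate choice possible, but the documents do not state one. Natalizumab is in Appendix 2 although neither the Background nor the eligibility criteria name it. Appendix 2 contains every agent named in the TNF, integrin and interleukin rows of Table 5-1 except golimumab, which looks more like an oversight. Even if it was intended, the rule still labels as naive a subject whom protocol Section 4.3.2 says is not.

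**The consequence is small.** This stands. The factor is a baseline variable, SAP Section 6.2.4 allows sparse strata to be merged, Section 4.1 has stratum discrepancies summarised and listed, and the subgroup analyses lie outside the alpha-controlled hypotheses.

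**The reach is limited.** This also stands. A reader might infer that the Maintenance biologic yes/no factor and the TNF-exposure subgroup are wrong too. Neither cites Appendix 2, so they are undefined on this point rather than wrong. Golimumab started during the study is also unaffected, because the treatment-failure rule in SAP Appendix 6 covers biologics without a closed list.

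**Conclusion.** The point holds as a minor, specific inconsistency. As written, Appendix 2 places golimumab-only subjects at zero exposures in the Cohort A CMH factor, the Cohort A and pooled subgroups and the baseline table. It also lowers subjects with golimumab plus one listed agent by one CMH stratum in either cohort.

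Three stronger readings are tempting and not supported:
- *Every golimumab-treated subject is in the wrong stratum.* Golimumab plus two or more listed agents stays at >1, and golimumab-only subjects in Cohort B stay at ≤1 in the CMH.
- *The primary result is biased.* Prior exposure is fixed before randomization and the same rule applies to all arms. The illustration shows no material change in power or type I error.
- *The number affected can be estimated from the 1,320 planned subjects.* The documents give no golimumab share, that total includes naive subjects who by definition had none, and not every exposed subject changes category.

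What remains is damage to naive/experienced labels, to the subgroup estimates built on them, and to agreement with the randomization strata. Its size depends on a prevalence that the documents do not report. The conclusion assumes that the database derivation follows Appendix 2 literally.

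**What to change.** Add golimumab and its biosimilars to SAP Appendix 2 as a TNF antagonist. State that the same list defines the Maintenance biologic yes/no factor in Section 6.2.4 and its subgroup in Section 6.2.7, and the prior TNF-exposure subgroup. If golimumab is left out on purpose, the SAP should say why and reconcile that with protocol Section 4.3.2.

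The cost is one table row, two cross-references and one line in the derivation program. No new data collection is specified for it, since treatment history is already recorded at screening. It should be done before unblinding, so that a primary-analysis stratum is not redefined afterwards.

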**Appendix 3. Crohn’s Disease Activity Index (CDAI) and Patient Reported Outcomes – 2 items (PRO2)**

The total CDAI score is a weighted sum of all 8 variables as specified in [Table 13-1](#), and the PRO2 scores will be assessed according to [Table 13-2](#) and [Table 13-3](#). Details for the calculations of CDAI and PRO2 scores at screening and post-screening visits are provided in this appendix.

